### 5.7.3 Contraception

MK-8628 may have adverse effects on a fetus in utero. Furthermore, it is not known if MK-8628 has transient adverse effects on the composition of sperm.

For this trial, male subjects will be considered to be of non-reproductive potential if they have azoospermia (whether due to having had a vasectomy or due to an underlying medical condition).

Female subjects will be considered of non-reproductive potential if they are either:

- 1) postmenopausal (defined as at least 12 months with no menses without an alternative medical cause; in women  $< 45$  years of age a high follicle-stimulating hormone (FSH) level in the postmenopausal range may be used to confirm a post-menopausal state in women not using hormonal contraception or hormonal replacement therapy. In the absence of 12 months of amenorrhea, a single FSH measurement is insufficient.);

OR

- 2) have had a hysterectomy and/or bilateral oophorectomy, bilateral salpingectomy, or bilateral tubal ligation/occlusion at least 6 weeks prior to screening;

OR

3) has a congenital or acquired condition that prevents childbearing.

Female and male subjects of reproductive potential must agree to avoid becoming pregnant or impregnating a partner, respectively, while receiving study drug MK-8628 and for 90 days after the last dose of study drug. Subjects must comply with one of the following:

1) practice abstinence† from heterosexual activity;

OR

2) use (or have their partner use) acceptable contraception during heterosexual activity.

Acceptable methods of contraception are‡:

Single method (one of the following is acceptable):

- intrauterine device (IUD)
- vasectomy of a female subject's sole male partner
- contraceptive rod implanted into the skin

Combination method (requires use of two of the following):

- diaphragm with spermicide (cannot be used in conjunction with cervical cap/spermicide)
- cervical cap with spermicide (nulliparous women only)
- contraceptive sponge (nulliparous women only)
- male condom or female condom (cannot be used together)
- hormonal contraceptive: oral contraceptive pill (estrogen/progestin pill or progestin-only pill), contraceptive skin patch, vaginal contraceptive ring, or subcutaneous contraceptive injection

†Abstinence (relative to heterosexual activity) can be used as the sole method of contraception if it is consistently employed as the subject's preferred and usual lifestyle and if considered acceptable by local regulatory agencies and ERCs/IRBs. Periodic abstinence (e.g., calendar, ovulation, sympto-thermal, post-ovulation methods, etc.) and withdrawal are not acceptable methods of contraception.

‡If a contraceptive method listed above is restricted by local regulations/guidelines, then it does not qualify as an acceptable method of contraception for subjects participating at sites in this country/region.

Subjects should be informed that taking the study medication may involve unknown risks to the fetus (unborn baby) if pregnancy were to occur during the study. In order to participate in the study, subjects of childbearing potential must adhere to the contraception requirement

(described above) from the day of study medication initiation (or 14 days prior to the initiation of study medication treatment [Day 1] for oral contraception) throughout the study period up to 90 days after the last dose of trial therapy. If there is any question that a subject of childbearing potential will not reliably comply with the requirements for contraception, that subject should not be entered into the study.

Monthly pregnancy testing is recommended per local standards if applicable.

**For countries (e.g., Sweden and Norway) or sites that follow the Clinical Trial Facilitation Group (CTFG) guidance, please use the following:**

MK-8628 may have adverse effects on a fetus in utero. Furthermore, it is not known if it may have transient adverse effects on the composition of sperm. Therefore, non-pregnant, non-breastfeeding women may only be enrolled if they are willing to follow the CTFG Guidance (Final Version 2014-09-15, Sections 4.1 and 4.2) for highly effective birth control as outlined below, or are considered to be highly unlikely to conceive. Highly unlikely to conceive is defined as 1) surgically sterilized, or 2) postmenopausal (a woman who is  $\geq 45$  years of age and has not had menses for greater than 1 year will be considered postmenopausal), or 3) not heterosexually active for the duration of the study. Subjects should use birth control methods that can achieve a failure rate of less than 1% per year when used consistently and correctly and are considered as highly effective birth control methods. Such methods include:

- Combined (estrogen and progestogen containing) hormonal contraception associated with inhibition of ovulation:
  - Oral
  - Intravaginal
  - Transdermal
- Progestogen-only hormonal contraception associated with inhibition of ovulation:
  - Oral
  - Injectable
  - Implantable
- Intrauterine device (IUD)
- Intrauterine hormone-releasing system (IUS)
- Bilateral tubal occlusion
- Vasectomised partner

- Sexual abstinence

Subjects should start using birth control from study Visit 1 throughout the study period up to 90 days after the last dose of study therapy.

Subjects should be informed that taking the study medication may involve unknown risks to the fetus (unborn baby) if pregnancy were to occur during the study. In order to participate in the study they must adhere to the contraception requirement (described above) for the duration of the study and during the follow-up period defined in Section 7.2.2 – Reporting of Pregnancy and Lactation to the Sponsor. If there is any question that a subject will not reliably comply with the requirements for contraception, that subject should not be entered into the study.

#### **5.7.4 Pregnancy**

If a subject inadvertently becomes pregnant while on treatment with MK-8628, the subject will immediately be discontinued from trial treatment. The site will contact the subject at least monthly and document the subject's status until the pregnancy has been completed or terminated. The outcome of the pregnancy will be reported to the SPONSOR without delay and within 24 hours if the outcome is a serious adverse experience (e.g., death, abortion, congenital anomaly, or other disabling or life-threatening complication to the mother or newborn). The study investigator will make every effort to obtain permission to follow the outcome of the pregnancy and report the condition of the fetus or newborn to the SPONSOR. If a male subject impregnates his female partner the study personnel at the site must be informed immediately and the pregnancy reported to the SPONSOR and followed as described above and in Section 7.2.2.

#### **5.7.5 Nursing Women**

It is unknown whether MK-8628 is excreted in human milk. Since many drugs are excreted in human milk, and because of the potential for serious adverse reactions in the nursing infant, subjects who are breast-feeding are not eligible for enrollment.

### **5.8 Subject Withdrawal/Discontinuation Criteria**

Subjects may withdraw consent at any time for any reason or be dropped from the trial at the discretion of the investigator should any untoward effect occur. In addition, a subject may be withdrawn by the investigator or the Sponsor if enrollment into the trial is inappropriate, the trial plan is violated, or for administrative and/or other safety reasons. Specific details regarding discontinuation or withdrawal procedures; including specific details regarding withdrawal from Future Biomedical Research, are provided in Section 7.1.4 – Other Procedures.

Subjects will continue study treatment until any of the following events at which point it will be definitively discontinued:

- Disease progression
- Unacceptable toxicity

- Subject withdrawal of consent
- Subject non-compliance
- Treatment interruption for > 2 weeks for any reason (except in the event of perceived benefit, with Sponsor agreement)
- Recurrence of DLT despite dose reduction (except in the event of perceived benefit, with Sponsor agreement)

However, in case of investigator's perceived benefit for the subject, treatment continuation can be considered with dose reduction despite delay/interruption > 2 weeks or reoccurrence of a DLT with the same intensity after one dose reduction. The perceived benefit of the investigator is defined by 1) any objective tumor response, or 2) any tumor regression not meeting standard response criteria, but which could improve with additional treatment, or 3) any symptomatic improvement, which, in the investigator's opinion, could not be achieved by other means. If, in the cases described above, DLT recurs with the same intensity despite one dose reduction, a second dose reduction may be considered. The decision should be discussed with the Sponsor, but the final decision must be made by the investigator. The reason for and date of dose reduction must be recorded in the eCRF and source documented in the subject's medical records.

In all cases, the reason for and date of study treatment discontinuation must be recorded in the eCRF and source documented in the subject's medical records. As far as possible, there should be only one reason for treatment discontinuation. If there are several (e.g. concomitant progressive disease and toxicity), the primary one must be reported. The subject must be followed up to establish whether the reason was an AE, and if so, this must be reported as such.

As far as possible, all examinations scheduled for the final study day must be performed for all subjects who receive the investigational product but who do not complete the study according to protocol.

The investigator must make every effort to contact subjects lost to follow-up, especially when a subject is treated in another non-study center.

## **5.9 Subject Replacement Strategy**

Subjects not evaluable for DLT (i.e. receiving less than 85% of the intended cumulative dose in Cycle 1 for any reason other than toxicity; < 18 days of treatment) and who do not experience DLT will be replaced.

A subject who discontinues from the trial for any other reason will not be replaced.

## **5.10 Beginning and End of the Trial**

The overall trial begins when the first subject signs the informed consent form. The overall trial ends when the last subject completes the last study-related phone-call or visit, discontinues from the trial or is lost to follow-up (i.e. the subject is unable to be contacted by the investigator).

### **5.11 Clinical Criteria for Early Trial Termination**

Early trial termination will be the result of the criteria specified below:

1. Incidence or severity of adverse drug reactions in this or other trials suggest a potential health hazard to subjects
2. Quality or quantity of data recording is inaccurate or incomplete
3. Poor adherence to protocol and regulatory requirements
4. Plans to modify or discontinue the development of the study drug

In the event of Sponsor decision to no longer supply study drug, ample notification will be provided so that appropriate adjustments to subject treatment can be made

## 6.0 TRIAL FLOW CHART

	Screening Phase	Treatment Phase Cycle = 21 days						End of Treatment	Post Treatment Phase		
		Cycle 1		Cycle 2	Cycle 3	Cycle 4	Cycle 5 and beyond		30 Day Post Treatment Safety Follow-up Visit	Follow-up Visits (AML) a	Follow-up Visits (DLBCL) a
Treatment Cycle/Title:	Pre-study / Screening (Visit 1)							Treatment Discontinuation Visit	30 Day Post Treatment Safety Follow-up Visit	Follow-up Visits (AML) a	Follow-up Visits (DLBCL) a
Cycle Day:		1	8	15	1	1	1	At the time of discontinuation	30 days post discontinuation	Every 6 weeks post discontinuation	Every 12 weeks post discontinuation
Scheduling Window Days:	-14 to -1	±3	±3	±3	±3	±3	±3		±3	±3	±7
Administrative Procedures											
Informed Consent	X										
Informed Consent for Future Biomedical Research	X										
Inclusion/Exclusion Criteria	X										
Subject Identification Card	X										
Demographics, Medical History	X										
Concomitant Medication Review	X	X	X	X	X	X	X	X	X		
Diagnosis & prior treatments for malignancy	X										
Baseline symptoms & complaints	X										
MK-8628 Administration/Dispensing											
MK-8628 Administration/Dispensing		BID continuously b at assigned dose level; Study drug will be dispensed on or prior to day 1 of each cycle.									
Clinical Procedures/Assessments											
Full Physical Examination	X	X						X			
Directed Physical Examination			X	X	X	X	X				
ECOG Performance Status (PS)	X	X	X	X	X	X	X	X			

	Screening Phase	Treatment Phase Cycle = 21 days						End of Treatment	Post Treatment Phase		
		Cycle 1		Cycle 2	Cycle 3	Cycle 4	Cycle 5 and beyond		30 Day Post Treatment Safety Follow-up Visit	Follow-up Visits (AML) a	Follow-up Visits (DLBCL) a
Treatment Cycle/Title:	Pre-study / Screening (Visit 1)										
Cycle Day:		1	8	15	1	1	1	At the time of discontinuation	30 days post discontinuation	Every 6 weeks post discontinuation	Every 12 weeks post discontinuation
Scheduling Window Days:	-14 to -1		±3	±3	±3	±3	±3		±3	±3	±7
Height	X										
Weight	X	X	X	X	X	X	X	X			
Vital Signs (heart rate, blood pressure, temperature)	X	X c	X d	X	X n						
12 Lead Electrocardiogram (ECG)	X	X c				X d		X e	X	X n	
Bone Marrow Aspiration / Biopsy: AML f	X				X	X					
Tumor Assessment & Response Evaluation: AML f				X	X	X	X			X a	
PET & CT Imaging (Neck, Chest, Abdomen, Pelvis): DLBCL g	X						X	X h			X a
Tumor Assessment & Response Evaluation: DLBCL g and Assessment of Lymphoma B Symptoms g							X	X h			X a
Adverse Events Monitoring	X	X	X	X	X	X	X	X	X i	X i	X i
Tumor Sample Submission j	X										
Laboratory Procedures/Assessments											
Complete Blood Count (CBC) k	X m	X	X	X	X	X	X	X	X n	X a	
PT-International Normalized Ratio (INR), aPTT, and Factor VII	X m	X	X	X	X	X	X	X	X n		
Serum Chemistry l	X m	X	X	X	X	X	X	X	X n		
Urinalysis	X	X	X	X	X	X	X	X	X n		

	Screening Phase	Treatment Phase Cycle = 21 days						End of Treatment	Post Treatment Phase		
		Cycle 1	Cycle 2	Cycle 3	Cycle 4	Cycle 5 and beyond	Treatment Discontinuation Visit		30 Day Post Treatment Safety Follow-up Visit	Follow-up Visits (AML) a	Follow-up Visits (DLBCL) a
Treatment Cycle/Title:	Pre-study / Screening (Visit 1)										
Cycle Day:		1	8	15	1	1	1	At the time of discontinuation	30 days post discontinuation	Every 6 weeks post discontinuation	Every 12 weeks post discontinuation
Scheduling Window Days:	-14 to -1	$\pm 3$	$\pm 3$	$\pm 3$	$\pm 3$	$\pm 3$	$\pm 3$		$\pm 3$	$\pm 3$	$\pm 7$
Urine or Serum Pregnancy Test – if applicable o	X o										
PK Blood Sampling		X p	X q	X q	X q						
PD Blood Sampling		X r	X s								
Blood for Genetic Analysis t		X									

- a. In subjects who discontinue study therapy without documented disease progression, every effort should be made to continue monitoring their disease status every 6 weeks ( $\pm 3$  days) for AML subjects and every 12 weeks ( $\pm 7$  days) for DLBCL subjects until (1) the start of new anti-cancer treatment, (2) documented disease progression, (3) death, or (4) the end of the study, whichever occurs first. If subjects have stable disease, partial response, or complete response, they should continue on this assessment schedule. Tumor response assessments should occur at any time where there is clinical suspicion of progression or relapse.
- b. MK-8628 is to be administered orally with water in a fasted state, and as part of a BID regimen (twice daily, approximately 12 hours apart). Subjects should not have food for 1 hour before or 3 hours after study drug administration. Dosing not performed at the same time ( $\pm 2$ h) as on other days should be skipped. Subjects are to be instructed that if they vomit or omit their dose in that time frame, it is not to be replaced.
- c. Collected at the following time points on day 1 of cycle 1: pre-dose, 1 hour post-dose, 2 hours post-dose.
- d. Collected prior to the subject dosing (pre-dose) on that day.
- e. Collected prior to the subject dosing (pre-dose) on day 1 of every odd treatment cycle (every 6 weeks) after cycle 3 day 1.
- f. AML tumor response assessments will be completed through the analysis of bone marrow aspiration samples and bone marrow biopsy samples (if necessary). See Section 7.1.2.7.1. Bone marrow analysis is required at screening, cycle 2 day 1, and cycle 3 day. Tumor response assessments will be conducted on day 1 of every cycle beyond cycle 3 through hematological analysis of peripheral blood. Evidence of response in peripheral blood may be confirmed by further bone marrow assessments as displayed in the tumor response criteria. The timing of tumor response assessments should follow calendar days and should not be adjusted for delays in cycle starts.
- g. DLBCL tumor response assessments will be completed through PET-CT and CT imaging analysis. See Section 7.1.2.7.2. The timing of tumor response assessments should follow calendar days and should not be adjusted for delays in cycle starts. The same imaging technique should be used in a subject throughout the trial. Routine imaging assessments (or bone marrow biopsy) performed outside of the scope of this study will be acceptable to complete the response criteria for DLBCL at screening, if performed  $\leq 4$  weeks prior to study entry. Assessment of lymphoma B symptoms should occur with each lymphoma disease response assessment.

- h. In subjects with an unconfirmed PD assessment, a radiological assessment should be performed at the time of treatment discontinuation. If previous scan was obtained within 4 weeks prior to the date of discontinuation, then a repeat scan at treatment discontinuation isn't mandatory. However, imaging should occur at any time where there is clinical suspicion of progression.
- i. Record all AEs occurring within 30 days after the last dose of trial treatment regardless when the Treatment Discontinuation Visit occurs. After 30 days, any drug related AE regardless of seriousness occurring outside of any reporting timeframes must be reported.
- j. Submission of tumor samples is applicable to subjects that sign the Future Biomedical Research consent form. A fresh bone marrow aspiration sample is required for AML subjects, in addition to a bone marrow trephine sample (if available). If a bone marrow trephine sample was not obtained (because not needed or unable to perform) or the bone marrow trephine sample is inadequate/poor quality, then only a bone marrow aspirate sample should be submitted. An archived or fresh lymph node biopsy sample without invasive procedure (e.g. superficial lymph node) is required for DLBCL subjects. If an archived lymph node sample is not available, the subject must agree to undergo a fresh tumor biopsy. All tumor biopsy samples will be sent to a central laboratory for further analysis.
- k. In cases of grade > 2 hematologic toxicity CBC will be performed twice a week until recovery to grade  $\leq$  2. In cases of neutropenia/thrombocytopenia grade 4, CBC will be performed at least every other day until recovery to grade  $\leq$  3. In cases of fever  $\geq$  38 °C, infection, purpura, or bleeding, additional CBC should be done as clinically indicated. In addition, bone marrow aspiration will be performed in all subjects with grade 4 thrombocytopenia lasting  $>$  3 days.
- l. See Section 7.1.3, from cycle 3 on, in the absence of  $\geq$  grade 2 abnormalities, these tests will be performed every cycle, otherwise they are to be done weekly until resolution to baseline levels or  $<$  grade 2.
- m. Screening CBC, PT-International Normalized Ratio (INR), aPTT, Factor VII and serum chemistry measurements must be taken within 7 days of the first dose of study treatment.
- n. Unresolved abnormal assessments that are drug related AEs should be followed until resolution.
- o. For women of reproductive potential, urine pregnancy test must be confirmed negative within 72 hours prior to receiving the first dose of study medication. If the urine test is positive or cannot be confirmed as negative, a serum pregnancy test will be required. The subject must be excluded in the event of a positive or borderline-positive serum test result.
- p. PK blood samples will be collected at pre-dose (before drug intake), 20 minutes post-dose ( $\pm$ 5 min), 1 hour post-dose ( $\pm$ 10 min), 2 hours 15minutes post-dose ( $\pm$ 10 min), 3hours15minutes post-dose ( $\pm$ 10 min), 8 hours post-dose ( $\pm$  1 hour), and 12 hours post-dose ( $\pm$  2 hours, before the second daily dose on day 1).
- q. PK blood samples will be collected at pre-dose (before drug intake).
- r. PD blood samples will be collected at pre-dose (before drug intake), 3 hours 15 minutes post-dose ( $\pm$ 10 min), 8 hours post-dose ( $\pm$  1 hour), and 12 hours post-dose ( $\pm$  2 hours, before the second daily dose on day 1).
- s. PD blood samples will be collected at pre-dose (before drug intake).
- t. Details for collection can be found in Section 7.1.3 Laboratory Procedures/Assessments.

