**Hematologic Toxicity:**

AML

1. Pancytopenia with a hypocellular bone marrow and no marrow blasts lasting for  $\geq 6$  weeks after the start of a cycle. For subjects with AML who have a suspected DLT in case of pancytopenia with a hypocellular bone marrow and no marrow blast on Day 22 bone marrow aspiration, the DLT window will be extended to the first 2 cycles or Day 42 for repeat bone marrow confirmation. However, enrollment of additional patients at this dose level should not be delayed during the extended window for DLT in this situation assuming a confirmed DLT for such a subject would not affect a dose escalation or de-escalation decision.

DLBCL

1. Grade 4 hematologic toxicity lasting  $\geq 7$  days, except thrombocytopenia  
Grade 4 thrombocytopenia of any duration  
Grade 3 thrombocytopenia is a DLT if associated with bleeding
2. Febrile or infection related neutropenia, Grade 3 or Grade 4

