### **5.2.2 Timing of Dose Administration**

MK-8628 is to be administered orally with water in a fasted state, and as part of a BID regimen (twice daily, approximately 12 hours apart). Subjects should not have food for 1 hour before or 3 hours after study drug administration.

Dosing not performed at the same time ( $\pm 2h$ ) as on other days should be skipped. Subjects are to be instructed that if they vomit or omit their dose in that time frame, it is not to be replaced. Capsules must not be opened or chewed.

A treatment cycle is 21 days (3 weeks). The subsequent cycle will begin on day 22 or after recovery from any AEs to baseline or Grade < 2 associated with the previous cycle.

Subjects should receive study treatment within 3 days following treatment allocation.

Details of the exact dose and time of administration will be documented in a validated subject diary and reported in the electronic case report form (eCRF).

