7.1.3.1.1 Complete Blood Count

In cases of grade > 2 hematologic toxicity, CBC will be performed twice a week until recovery to grade ≤ 2. In cases of neutropenia/thrombocytopenia grade 4, CBC will be performed at least every other day until recovery to grade ≤ 3. In addition, in cases of thrombocytopenia grade 4 lasting > 3 days, a bone marrow aspiration is to be performed. In cases of fever ≥ 38 °C, infection, purpura or bleeding, additional CBC should be done as clinically indicated.

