#### 7.1.3.2 Pharmacokinetic/Pharmacodynamic Evaluations

##### 7.1.3.2.1 PK Sample Collection (Plasma)

Samples will be collected on day 1 and three additional steady-state trough concentrations will be collected 1, 2 and 3 weeks after the first treatment intake.

The timing of the PK sample collections is as follows (see also [Table 8](#) below). Seven blood samples will be collected on **Day 1 of Cycle 1**: immediately prior to the first dose (**T0**) and **20 min $\pm$ 5min**, **1h $\pm$ 10min**, **2h15min $\pm$ 10min**, **3h15min $\pm$ 10min**, **8h $\pm$ 1h**, and **12h $\pm$ 2 hours** (immediately before the second daily dose on day 1). Subjects will either remain in the clinical research unit (CRU), or be hospitalized, for a minimum of 12 $\pm$ 2hours hours for PK sampling on day 1.

In addition, a single blood sample will be collected from all subject immediately before drug intake on **days 8** ( $\pm$ 1 days), **15** ( $\pm$ 2 days), **and 22** ( $\pm$ 3 days) to evaluate steady-state trough concentrations. Note: On these three days, it is critical that the subject withhold the morning dose until after the PK sample is collected in the clinic. Every effort should be made to collect the sample approximately 12h after the previous evening dose. The timing of the previous dose should be recorded. See [Table 8](#).

Table 8 PK Sample Collection Timing

PK Sample #	Visit	Time of collection
1	Cycle 1 Day 1	T0: Pre-morning dose
2	Cycle 1 Day 1	20 min $\pm$ 5 min post-morning dose
3	Cycle 1 Day 1	1 hr $\pm$ 10 min post-morning dose
4	Cycle 1 Day 1	2 hr 15 min $\pm$ 10 min post-morning dose
5	Cycle 1 Day 1	3 hr 15 min $\pm$ 10 min post-morning dose
6	Cycle 1 Day 1	8 hr $\pm$ 1 hr post-morning dose
7	Cycle 1 Day 1	12 hr $\pm$ 2 hours post-morning dose
8	Cycle 1 Day 8	Pre-morning dose
9	Cycle 1 Day 15	Pre-morning dose
10	Cycle 1 Day 22 (Cycle 2 Day 1)	Pre-morning dose

In total, ten blood samples of 3.0 mL each will be collected, i.e. approximately 30 mL of blood will be drawn per subject treated in the BID regimen from a peripheral venous access for PK analysis.

Sample collection, storage and shipment instructions for plasma samples will be provided in the Procedure Manual.

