## 8.4 Analysis Endpoints

### 8.4.1 Safety Endpoints

The primary safety objective of this trial is to estimate proportion of subjects experiencing at least one DLT in cycle 1 (day 1 to 21) for each of the regimens and tumor type independently.

Other safety endpoints include incidence, severity and relationship of AEs, laboratory abnormalities, SAEs, discontinuations due to AEs, dose adaptations due to AEs

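### The Day 1–21 DLT period can be closed by labs drawn on Day 19, and the ±3-day visit windows let Cycle 1 blood counts fall 12 to 13 days apart, so silent laboratory DLTs can go uncounted

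*Combined protocol and SAP*

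**What the plan says.** - Section 8.4.1 sets the primary safety objective: to "estimate proportion of subjects experiencing at least one DLT in cycle 1 (day 1 to 21"), for each regimen and tumor type.
- The Section 6.0 flow chart has a row "Scheduling Window Days" showing ±3 for Cycle 1 Day 8, Cycle 1 Day 15 and Cycle 2 Day 1. CBC, coagulation and chemistry are marked at Cycle 1 Days 1, 8 and 15, then on Day 1 of each later cycle. No separate CBC window is given.
- Section 7.1.2.7.1 repeats ±3 for Cycle 2 Day 1 (AML response assessment).
- Section 7.1.3.2.1 says "a single blood sample will be collected from all subject immediately before drug intake on" Day 8 (±1), Day 15 (±2) and Day 22 (±3). Its Table 8 labels the last of these "Cycle 1 Day 22 (Cycle 2 Day 1").
- Section 5.2.2 says: "The subsequent cycle will begin on day 22 or after recovery from any AEs". It allows no minus days.
- Section 5.2.1.3 makes "Grade 4 thrombocytopenia of any duration" a DLT in DLBCL, as well as other Grade 4 hematologic toxicity lasting at least 7 days. In both cohorts, a Grade 3–4 laboratory abnormality persisting more than a week is a DLT.
- Section 8.5.1 counts a subject as DLT-evaluable after 85% of the planned dose (18 days) or a DLT.

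**The concern.** A DLT defined by a laboratory value exists in the data only if someone draws blood while the value is abnormal. The plan defines its endpoint over 21 days, but its windows let the last scheduled draw precede the end of that period and let the draws inside it spread well beyond a week. Nothing in the plan sets a maximum interval between counts, or requires labs on or after Day 21 before a subject is called DLT-free.

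The stakes are the Table 4 decisions. With six subjects one event changes the action: 0/6 is Escalate and 1/6 is Stay; 2/6 is Stay and 3/6 is De-escalate. Missed events can only lower the observed rate. Section 4.2.2 reports thrombocytopenia as the prevalent DLT in the non-leukemia cohort of the earlier study, so the exposed event is the expected one.

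**Working it through.** **Plan's own figure.** 0.85 × 21 = 17.85, rounded up to 18 days, agrees with Sections 5.9 and 8.5.1 (18/21 = 85.7%).

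**Visit dates, flow-chart windows** (Day 1 fixed as the first dose; Cycle 2 Day 1 = Day 22; Cycle 3 Day 1 = Day 43, as in Section 5.5.1):
- Day 8 visit: Days 5–11. Day 15 visit: Days 12–18. Cycle 2 Day 1: Days 19–25. Cycle 3 Day 1: Days 40–46.

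**Closing visit.** 22 − 3 = Day 19. Eighteen dosing days (Days 1–18) fit before it, so the subject is already evaluable. The next scheduled count is 40 − 19 = 21 to 46 − 19 = 27 days later. Days 20 and 21 belong to the endpoint but have no scheduled labs.

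**Longest gap** = (later day + window) − (earlier day − window):

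| Windows | Day 1 to 8 | Day 8 to 15 | Day 15 to 22 |
|---|---|---|---|
| Nominal days | 7 | 7 | 7 |
| Flow chart (±3, ±3, ±3) | 11 − 1 = 10 | 18 − 5 = 13 | 25 − 12 = 13 |
| CBC drawn with PK (±1, ±2, ±3) | 9 − 1 = 8 | 17 − 7 = 10 | 25 − 13 = 12 |

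Thirteen is not a hard ceiling. Under Section 5.2.2 an unresolved Grade 2 event can delay Cycle 2 Day 1 without triggering extra counts.

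**What a long gap does.** Assume a silent episode of d days with onset uniform within a gap of g days. It falls wholly between counts with probability (g − d)/g:
- d = 7: 0% at g = 7; 5/12 = 42% at g = 12; 6/13 = 46% at g = 13.
- d = 3: 4/7 = 57%; 9/12 = 75%; 10/13 = 77%.

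Exact weekly counts guarantee a draw during a 7-day episode. The windows remove that guarantee. For shorter episodes weekly counts give no guarantee either.

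**Averaged over Cycle 1.** Assume integer days, each visit equally likely on any day of its window, onset equally likely on Days 2–21 and no symptoms. All combinations were enumerated (for the flow chart, 7 × 7 × 7 = 343 visit patterns × 20 onset days).
- 5-day episode: 14/20 = 70% seen at nominal days, 63% with flow-chart windows.
- 7-day episode: 20/20 = 100% at nominal days, 82% with flow-chart windows.

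**Effect on escalation, illustration only.** Take a true DLT rate of 25% and suppose every DLT is a silent episode of the stated length, which exaggerates the effect. P(0/6) = (1 − 0.25 × share seen)^6:
- 5-day: 0.825^6 = 31.5% at nominal days; (1 − 0.25 × 0.631)^6 = 35.7% with ±3.
- 7-day: 0.75^6 = 17.8% at nominal days; (1 − 0.25 × 0.821)^6 = 25.2% with ±3.

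**The case against.** Several counter-arguments have force.

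- **PK windows.** The flow chart puts PK sampling in the same visit columns as the CBC, and Section 7.1.3.2.1 holds Days 8 and 15 to ±1 and ±2. If one draw serves both, Days 5, 12 and 18 are not compliant and the maximum is 12 days. This stands, but no text ties the CBC to the PK draw, and Day 22 keeps ±3 there too, so a Day 19 closing visit remains allowed.
- **Other safeguards.** Section 7.1.3.1.1 says that for grade > 2 "hematologic toxicity, CBC will be performed twice a week until recovery to grade" ≤ 2, and it adds counts for fever, infection, purpura or bleeding. Section 5.5.1 asks for at least weekly counts in subjects on anticoagulant or antiaggregant therapy. Section 7.1 allows unscheduled procedures. These help once there is a sign, or in that subset. They do not find a silent nadir in other subjects.
- **Scope.** A reader might infer that DLTs in general are missed. The documents do not support that. The AML hematologic DLT is marrow-based, lasts at least 6 weeks and has a window extended to Day 42. Symptomatic events can still be recorded by onset date, because Section 7.2 collects all adverse events through 30 days after treatment.
- **Size.** A reader might set 5/7 = 71% detection of a 5-day episode at weekly spacing against 5/13 = 38% at 13 days, or assume 30% of DLTs are missed and read the rise in P(0/6) from 17.8% to 31.5% as the cost of the windows. Neither measures the window effect. The first considers only onsets inside the longest gap. The second uses a loss that exact weekly visits already produce for a 5-day episode (2/7 = 29%).
- **Closed enrollment.** Section 1.0 says enrollment has ended and one subject remains, so no escalation decision is left to protect. The flaw still bears on how the DLT estimate is read.

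**Conclusion.** The point holds as a design weakness with a cheap remedy. Two facts follow directly from the documents: the visit closing a 21-day endpoint may occur on Day 19, in conflict with Section 5.2.2, and scheduled counts may be 13 days apart (12 if tied to the PK sample). An evaluable subject can therefore be counted DLT-free with Days 20–21 unobserved.

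The exposure is limited to silent laboratory DLTs: DLBCL Grade 4 thrombocytopenia of any duration, other Grade 4 cytopenia of at least 7 days, and chemistry abnormalities in both cohorts. The direction is toward undercounting. The documents give neither episode durations nor the share of DLTs that are silent, so the size is unknown. Under the stated assumptions the windows lower average detection from 70% to 63% for 5-day episodes and from 100% to 82% for 7-day episodes. The maximum of 56 subjects and the Table 11 intervals do not depend on the windows, but the event counts entered into them do.

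**What to change.** - In Sections 5.2.1.3 and 8.5.1, state that a subject without a DLT counts as DLT-free only after a CBC and chemistry on or after Day 22.
- In Section 6.0, give these closing labs no minus days and a short plus side, for example 0/+1. A 0/+3 window would still leave 25 − 14 = 11 days with Day 15 at ±1, or 25 − 13 = 12 with Day 15 at ±2.
- Hold the Day 8 and Day 15 CBC and chemistry at least to the existing PK windows (±1 and ±2). With 0/+1 at Day 22 the longest gap becomes 23 − 13 = 10 days. By the same enumeration, detection is about 67% for a 5-day and 91% for a 7-day episode. This improves detection but does not restore the weekly guarantee.
- Reconcile Sections 5.2.2, 6.0, 7.1.2.7.1 and 7.1.3.2.1 on Day 22/Cycle 2 Day 1. The change proposed here concerns only the labs that close the DLT period; when Cycle 2 dosing may start is for the sponsor to settle.
- As enrollment has closed, report in the clinical study report how many DLT-evaluable subjects had their closing labs before Day 22, and the longest interval between counts in Cycle 1.

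Cost: wording changes, slightly less scheduling freedom and probably a few more minor window deviations in Cycle 1. No visits or samples are added.
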